Fatigue or Malaise Report only one	Symptoms causing no or minimal interference with usual social & functional activities	Symptoms causing greater than minimal interference with usual social & functional activities	Symptoms causing inability to perform usual social & functional activities	Incapacitating symptoms of fatigue or malaise causing inability to perform basic self-care functions
Fever (non-axillary temperatures only)	38.0 to $< 38.6^{\circ}\text{C}$ or 100.4 to $< 101.5^{\circ}\text{F}$	≥ 38.6 to $< 39.3^{\circ}\text{C}$ or ≥ 101.5 to $< 102.7^{\circ}\text{F}$	≥ 39.3 to $< 40.0^{\circ}\text{C}$ or ≥ 102.7 to $< 104.0^{\circ}\text{F}$	$\geq 40.0^{\circ}\text{C}$ or $\geq 104.0^{\circ}\text{F}$
Pain¹⁰ (not associated with study agent injections and not specified elsewhere) Specify location	Pain causing no or minimal interference with usual social & functional activities	Pain causing greater than minimal interference with usual social & functional activities	Pain causing inability to perform usual social & functional activities	Disabling pain causing inability to perform basic self-care functions OR Hospitalization indicated
Serum Sickness¹¹	Mild signs and symptoms	Moderate signs and symptoms AND Intervention indicated (e.g., antihistamines)	Severe signs and symptoms AND Higher level intervention indicated (e.g., steroids or IV fluids)	Life-threatening consequences (e.g., requiring pressor or ventilator support)

⁹ Definition: A disorder characterized by nausea, headache, tachycardia, hypotension, rash, and/or shortness of breath.

¹⁰ For pain associated with injections or infusions, see the *Site Reactions to Injections and Infusions* section (page 23).

¹¹ Definition: A disorder characterized by fever, arthralgia, myalgia, skin eruptions, lymphadenopathy, marked discomfort, and/or dyspnea.

Systemic

PARAMETER	GRADE 1 MILD	GRADE 2 MODERATE	GRADE 3 SEVERE	GRADE 4 POTENTIALLY LIFE- THREATENING
Underweight¹² > 5 to 19 years of age	NA	WHO BMI z-score < -2 to ≤ -3	WHO BMI z-score < -3	WHO BMI z-score < -3 with life-threatening consequences
2 to 5 years of age	NA	WHO Weight-for- height z-score < -2 to ≤ -3	WHO Weight-for- height z-score < -3	WHO Weight-for-height z-score < -3 with life- threatening consequences
< 2 years of age	NA	WHO Weight-for- length z-score < -2 to ≤ -3	WHO Weight-for- length z-score < -3	WHO Weight-for-length z-score < -3 with life- threatening consequences
Weight Loss (excludes postpartum weight loss)	NA	5 to < 9% loss in body weight from baseline	≥ 9 to < 20% loss in body weight from baseline	≥ 20% loss in body weight from baseline OR Aggressive intervention indicated (e.g., tube feeding, total parenteral nutrition)

¹² WHO reference tables may be accessed by clicking the desired age range or by accessing the following URLs: http://www.who.int/growthref/who2007_bmi_for_age/en/ for participants > 5 to 19 years of age and http://www.who.int/childgrowth/standards/chart_catalogue/en/ for those ≤ 5 years of age.

Urinary

PARAMETER	GRADE 1 MILD	GRADE 2 MODERATE	GRADE 3 SEVERE	GRADE 4 POTENTIALLY LIFE- THREATENING
Urinary Tract Obstruction	NA	Signs or symptoms of urinary tract obstruction without hydronephrosis or renal dysfunction	Signs or symptoms of urinary tract obstruction with hydronephrosis or renal dysfunction	Obstruction causing life-threatening consequences

Site Reactions to Injections and Infusions

PARAMETER	GRADE 1 MILD	GRADE 2 MODERATE	GRADE 3 SEVERE	GRADE 4 POTENTIALLY LIFE- THREATENING
Injection Site Pain or Tenderness Report only one	Pain or tenderness causing no or minimal limitation of use of limb	Pain or tenderness causing greater than minimal limitation of use of limb	Pain or tenderness causing inability to perform usual social & functional activities	Pain or tenderness causing inability to perform basic self-care function OR Hospitalization indicated
Injection Site Erythema or Redness¹³ Report only one > 15 years of age	2.5 to < 5 cm in diameter OR 6.25 to < 25 cm ² surface area AND Symptoms causing no or minimal interference with usual social & functional activities	≥ 5 to < 10 cm in diameter OR ≥ 25 to < 100 cm ² surface area OR Symptoms causing greater than minimal interference with usual social & functional activities	≥ 10 cm in diameter OR ≥ 100 cm ² surface area OR Ulceration OR Secondary infection OR Phlebitis OR Sterile abscess OR Drainage OR Symptoms causing inability to perform usual social & functional activities	Potentially life-threatening consequences (e.g., abscess, exfoliative dermatitis, necrosis involving dermis or deeper tissue)
≤ 15 years of age	≤ 2.5 cm in diameter	> 2.5 cm in diameter with < 50% surface area of the extremity segment involved (e.g., upper arm or thigh)	≥ 50% surface area of the extremity segment involved (e.g., upper arm or thigh) OR Ulceration OR Secondary infection OR Phlebitis OR Sterile abscess OR Drainage	Potentially life-threatening consequences (e.g., abscess, exfoliative dermatitis, necrosis involving dermis or deeper tissue)
Injection Site Induration or Swelling Report only one > 15 years of age	Same as for Injection Site Erythema or Redness , > 15 years of age	Same as for Injection Site Erythema or Redness , > 15 years of age	Same as for Injection Site Erythema or Redness , > 15 years of age	Same as for Injection Site Erythema or Redness , > 15 years of age
≤ 15 years of age	Same as for Injection Site Erythema or Redness , ≤ 15 years of age	Same as for Injection Site Erythema or Redness , ≤ 15 years of age	Same as for Injection Site Erythema or Redness , ≤ 15 years of age	Same as for Injection Site Erythema or Redness , ≤ 15 years of age
Injection Site Pruritus	Itching localized to the injection site that is relieved spontaneously or in < 48 hours of treatment	Itching beyond the injection site that is not generalized OR Itching localized to the injection site requiring ≥ 48 hours treatment	Generalized itching causing inability to perform usual social & functional activities	NA

¹³ Injection Site Erythema or Redness should be evaluated and graded using the greatest single diameter or measured surface area.

Laboratory Values

Chemistries

PARAMETER	GRADE 1 MILD	GRADE 2 MODERATE	GRADE 3 SEVERE	GRADE 4 POTENTIALLY LIFE-THREATENING
Acidosis	NA	pH \geq 7.3 to < LLN	pH < 7.3 without life-threatening consequences	pH < 7.3 with life-threatening consequences
Albumin, Low (g/dL; g/L)	3.0 to < LLN 30 to < LLN	\geq 2.0 to < 3.0 \geq 20 to < 30	< 2.0 < 20	NA
Alkaline Phosphatase, High	1.25 to < 2.5 x ULN	2.5 to < 5.0 x ULN	5.0 to < 10.0 x ULN	\geq 10.0 x ULN
Alkalosis	NA	pH > ULN to \leq 7.5	pH > 7.5 without life-threatening consequences	pH > 7.5 with life-threatening consequences
ALT or SGPT, High Report only one	1.25 to < 2.5 x ULN	2.5 to < 5.0 x ULN	5.0 to < 10.0 x ULN	\geq 10.0 x ULN
Amylase (Pancreatic) or Amylase (Total), High Report only one	1.1 to < 1.5 x ULN	1.5 to < 3.0 x ULN	3.0 to < 5.0 x ULN	\geq 5.0 x ULN
AST or SGOT, High Report only one	1.25 to < 2.5 x ULN	2.5 to < 5.0 x ULN	5.0 to < 10.0 x ULN	\geq 10.0 x ULN
Bicarbonate, Low (mEq/L; mmol/L)	16.0 to < LLN 16.0 to < LLN	11.0 to < 16.0 11.0 to < 16.0	8.0 to < 11.0 8.0 to < 11.0	< 8.0 < 8.0
Bilirubin Direct Bilirubin¹⁴, High > 28 days of age	NA	NA	> ULN	> ULN with life-threatening consequences (e.g., signs and symptoms of liver failure)
\leq 28 days of age	ULN to \leq 1 mg/dL	> 1 to \leq 1.5 mg/dL	> 1.5 to \leq 2 mg/dL	> 2 mg/dL
Total Bilirubin, High > 28 days of age	1.1 to < 1.6 x ULN	1.6 to < 2.6 x ULN	2.6 to < 5.0 x ULN	\geq 5.0 x ULN
\leq 28 days of age	See Appendix A. Total Bilirubin for Term and Preterm Neonates	See Appendix A. Total Bilirubin for Term and Preterm Neonates	See Appendix A. Total Bilirubin for Term and Preterm Neonates	See Appendix A. Total Bilirubin for Term and Preterm Neonates
Calcium, High (mg/dL; mmol/L)				
\geq 7 days of age	10.6 to < 11.5 2.65 to < 2.88	11.5 to < 12.5 2.88 to < 3.13	12.5 to < 13.5 3.13 to < 3.38	\geq 13.5 \geq 3.38
< 7 days of age	11.5 to < 12.4 2.88 to < 3.10	12.4 to < 12.9 3.10 to < 3.23	12.9 to < 13.5 3.23 to < 3.38	\geq 13.5 \geq 3.38

Chemistries

PARAMETER	GRADE 1 MILD	GRADE 2 MODERATE	GRADE 3 SEVERE	GRADE 4 POTENTIALLY LIFE-THREATENING
Calcium (Ionized), High (mg/dL; mmol/L)	> ULN to < 6.0 > ULN to < 1.5	6.0 to < 6.4 1.5 to < 1.6	6.4 to < 7.2 1.6 to < 1.8	≥ 7.2 ≥ 1.8
Calcium, Low (mg/dL; mmol/L) ≥ 7 days of age	7.8 to < 8.4 1.95 to < 2.10	7.0 to < 7.8 1.75 to < 1.95	6.1 to < 7.0 1.53 to < 1.75	< 6.1 < 1.53
< 7 days of age	6.5 to < 7.5 1.63 to < 1.88	6.0 to < 6.5 1.50 to < 1.63	5.50 to < 6.0 1.38 to < 1.50	< 5.50 < 1.38
Calcium (Ionized), Low (mg/dL; mmol/L)	< LLN to 4.0 < LLN to 1.0	3.6 to < 4.0 0.9 to < 1.0	3.2 to < 3.6 0.8 to < 0.9	< 3.2 < 0.8
Cardiac Troponin I, High	NA	NA	NA	Levels consistent with myocardial infarction or unstable angina as defined by the local laboratory
Creatine Kinase, High	3 to < 6 x ULN	6 to < 10 x ULN	10 to < 20 x ULN	≥ 20 x ULN
Creatinine, High	1.1 to 1.3 x ULN	> 1.3 to 1.8 x ULN OR Increase of > 0.3 mg/dL above baseline	> 1.8 to < 3.5 x ULN OR Increase of 1.5 to < 2.0 x above baseline	≥ 3.5 x ULN OR Increase of ≥ 2.0 x above baseline
Creatinine Clearance¹⁵ or eGFR, Low Report only one	NA	< 90 to 60 ml/min or ml/min/1.73 m ² OR 10 to < 30% decrease from baseline	< 60 to 30 ml/min or ml/min/1.73 m ² OR ≥ 30 to < 50% decrease from baseline	< 30 ml/min or ml/min/1.73 m ² OR ≥ 50% decrease from baseline or dialysis needed
Glucose (mg/dL; mmol/L) Fasting, High	110 to 125 6.11 to < 6.95	> 125 to 250 6.95 to < 13.89	> 250 to 500 13.89 to < 27.75	> 500 ≥ 27.75
Nonfasting, High	116 to 160 6.44 to < 8.89	> 160 to 250 8.89 to < 13.89	> 250 to 500 13.89 to < 27.75	> 500 ≥ 27.75
Glucose, Low (mg/dL; mmol/L) ≥ 1 month of age	55 to 64 3.05 to 3.55	40 to < 55 2.22 to < 3.05	30 to < 40 1.67 to < 2.22	< 30 < 1.67
< 1 month of age	50 to 54 2.78 to 3.00	40 to < 50 2.22 to < 2.78	30 to < 40 1.67 to < 2.22	< 30 < 1.67
Lactate, High	ULN to < 2.0 x ULN without acidosis	≥ 2.0 x ULN without acidosis	Increased lactate with pH < 7.3 without life- threatening consequences	Increased lactate with pH < 7.3 with life- threatening consequences

¹⁵ Use the applicable formula (i.e., Cockcroft-Gault in mL/min or Schwartz in mL/min/1.73m²).

Chemistries

PARAMETER	GRADE 1 MILD	GRADE 2 MODERATE	GRADE 3 SEVERE	GRADE 4 POTENTIALLY LIFE- THREATENING
Lipase, High	1.1 to < 1.5 x ULN	1.5 to < 3.0 x ULN	3.0 to < 5.0 x ULN	≥ 5.0 x ULN
Lipid Disorders (mg/dL; mmol/L)				
Cholesterol, Fasting, High ≥ 18 years of age	200 to < 240 5.18 to < 6.19	240 to < 300 6.19 to < 7.77	≥ 300 ≥ 7.77	NA
< 18 years of age	170 to < 200 4.40 to < 5.15	200 to < 300 5.15 to < 7.77	≥ 300 ≥ 7.77	NA
LDL, Fasting, High ≥ 18 years of age	130 to < 160 3.37 to < 4.12	160 to < 190 4.12 to < 4.90	≥ 190 ≥ 4.90	NA
> 2 to < 18 years of age	110 to < 130 2.85 to < 3.34	130 to < 190 3.34 to < 4.90	≥ 190 ≥ 4.90	NA
Triglycerides, Fasting, High	150 to 300 1.71 to 3.42	>300 to 500 >3.42 to 5.7	>500 to < 1,000 >5.7 to 11.4	> 1,000 > 11.4
Magnesium¹⁶, Low (mEq/L; mmol/L)	1.2 to < 1.4 0.60 to < 0.70	0.9 to < 1.2 0.45 to < 0.60	0.6 to < 0.9 0.30 to < 0.45	< 0.6 < 0.30
Phosphate, Low (mg/dL; mmol/L)				
> 14 years of age	2.0 to < LLN 0.81 to < LLN	1.4 to < 2.0 0.65 to < 0.81	1.0 to < 1.4 0.32 to < 0.65	< 1.0 < 0.32
1 to 14 years of age	3.0 to < 3.5 0.97 to < 1.13	2.5 to < 3.0 0.81 to < 0.97	1.5 to < 2.5 0.48 to < 0.81	< 1.5 < 0.48
< 1 year of age	3.5 to < 4.5 1.13 to < 1.45	2.5 to < 3.5 0.81 to < 1.13	1.5 to < 2.5 0.48 to < 0.81	< 1.5 < 0.48
Potassium, High (mEq/L; mmol/L)	5.6 to < 6.0 5.6 to < 6.0	6.0 to < 6.5 6.0 to < 6.5	6.5 to < 7.0 6.5 to < 7.0	≥ 7.0 ≥ 7.0
Potassium, Low (mEq/L; mmol/L)	3.0 to < 3.4 3.0 to < 3.4	2.5 to < 3.0 2.5 to < 3.0	2.0 to < 2.5 2.0 to < 2.5	< 2.0 < 2.0
Sodium, High (mEq/L; mmol/L)	146 to < 150 146 to < 150	150 to < 154 150 to < 154	154 to < 160 154 to < 160	≥ 160 ≥ 160
Sodium, Low (mEq/L; mmol/L)	130 to < 135 130 to < 135	125 to < 130 125 to < 135	121 to < 125 121 to < 125	≤ 120 ≤ 120
Uric Acid, High (mg/dL; mmol/L)	7.5 to < 10.0 0.45 to < 0.59	10.0 to < 12.0 0.59 to < 0.71	12.0 to < 15.0 0.71 to < 0.89	≥ 15.0 ≥ 0.89

¹⁶ To convert a magnesium value from mg/dL to mmol/L, laboratories should multiply by 0.4114.

Hematology

PARAMETER	GRADE 1 MILD	GRADE 2 MODERATE	GRADE 3 SEVERE	GRADE 4 POTENTIALLY LIFE- THREATENING
Absolute CD4+ Count, Low (cell/mm ³ ; cells/L) > 5 years of age (not HIV infected)	300 to < 400 300 to < 400	200 to < 300 200 to < 300	100 to < 200 100 to < 200	< 100 < 100
Absolute Lymphocyte Count, Low (cell/mm ³ ; cells/L) > 5 years of age (not HIV infected)	600 to < 650 0.600 x 10 ⁹ to < 0.650 x 10 ⁹	500 to < 600 0.500 x 10 ⁹ to < 0.600 x 10 ⁹	350 to < 500 0.350 x 10 ⁹ to < 0.500 x 10 ⁹	< 350 < 0.350 x 10 ⁹
Absolute Neutrophil Count (ANC), Low (cells/mm ³ ; cells/L) > 7 days of age	800 to 1,000 0.800 x 10 ⁹ to 1.000 x 10 ⁹	600 to 799 0.600 x 10 ⁹ to 0.799 x 10 ⁹	400 to 599 0.400 x 10 ⁹ to 0.599 x 10 ⁹	< 400 < 0.400 x 10 ⁹
2 to 7 days of age	1,250 to 1,500 1.250 x 10 ⁹ to 1.500 x 10 ⁹	1,000 to 1,249 1.000 x 10 ⁹ to 1.249 x 10 ⁹	750 to 999 0.750 x 10 ⁹ to 0.999 x 10 ⁹	< 750 < 0.750 x 10 ⁹
≤ 1 day of age	4,000 to 5,000 4.000 x 10 ⁹ to 5.000 x 10 ⁹	3,000 to 3,999 3.000 x 10 ⁹ to 3.999 x 10 ⁹	1,500 to 2,999 1.500 x 10 ⁹ to 2.999 x 10 ⁹	< 1,500 < 1.500 x 10 ⁹
Fibrinogen, Decreased (mg/dL; g/L)	100 to < 200 1.00 to < 2.00 OR 0.75 to < 1.00 x LLN	75 to < 100 0.75 to < 1.00 OR ≥ 0.50 to < 0.75 x LLN	50 to < 75 0.50 to < 0.75 OR 0.25 to < 0.50 x LLN	< 50 < 0.50 OR < 0.25 x LLN OR Associated with gross bleeding
Hemoglobin¹⁷, Low (g/dL; mmol/L) ¹⁸ ≥ 13 years of age (male only)	10.0 to 10.9 6.19 to 6.76	9.0 to < 10.0 5.57 to < 6.19	7.0 to < 9.0 4.34 to < 5.57	< 7.0 < 4.34
≥ 13 years of age (female only)	9.5 to 10.4 5.88 to 6.48	8.5 to < 9.5 5.25 to < 5.88	6.5 to < 8.5 4.03 to < 5.25	< 6.5 < 4.03

¹⁷ Male and female sex are defined as sex at birth.

¹⁸ The conversion factor used to convert g/dL to mmol/L is 0.6206 and is the most commonly used conversion factor. For grading hemoglobin results obtained by an analytic method with a conversion factor other than 0.6206, the result must be converted to g/dL using the appropriate conversion factor for the particular laboratory.

Hematology

PARAMETER	GRADE 1 MILD	GRADE 2 MODERATE	GRADE 3 SEVERE	GRADE 4 POTENTIALLY LIFE- THREATENING
57 days of age to < 13 years of age (male and female)	9.5 to 10.4 5.88 to 6.48	8.5 to < 9.5 5.25 to < 5.88	6.5 to < 8.5 4.03 to < 5.25	< 6.5 < 4.03
36 to 56 days of age (male and female)	8.5 to 9.6 5.26 to 5.99	7.0 to < 8.5 4.32 to < 5.26	6.0 to < 7.0 3.72 to < 4.32	< 6.0 < 3.72
22 to 35 days of age (male and female)	9.5 to 11.0 5.88 to 6.86	8.0 to < 9.5 4.94 to < 5.88	6.7 to < 8.0 4.15 to < 4.94	< 6.7 < 4.15
8 to ≤ 21 days of age (male and female)	11.0 to 13.0 6.81 to 8.10	9.0 to < 11.0 5.57 to < 6.81	8.0 to < 9.0 4.96 to < 5.57	< 8.0 < 4.96
≤ 7 days of age (male and female)	13.0 to 14.0 8.05 to 8.72	10.0 to < 13.0 6.19 to < 8.05	9.0 to < 10.0 5.59 to < 6.19	< 9.0 < 5.59
INR, High (not on anticoagulation therapy)	1.1 to < 1.5 x ULN	1.5 to < 2.0 x ULN	2.0 to < 3.0 x ULN	≥ 3.0 x ULN
Methemoglobin (% hemoglobin)	5.0 to < 10.0%	10.0 to < 15.0%	15.0 to < 20.0%	≥ 20.0%
PTT, High (not on anticoagulation therapy)	1.1 to < 1.66 x ULN	1.66 to < 2.33 x ULN	2.33 to < 3.00 x ULN	≥ 3.00 x ULN
Platelets, Decreased (cells/mm ³ ; cells/L)	100,000 to < 124,999 100.000 x 10⁹ to < 124.999 x 10⁹	50,000 to < 100,000 50.000 x 10⁹ to < 100.000 x 10⁹	25,000 to < 50,000 25.000 x 10⁹ to < 50.000 x 10⁹	< 25,000 < 25.000 x 10 ⁹
PT, High (not on anticoagulation therapy)	1.1 to < 1.25 x ULN	1.25 to < 1.50 x ULN	1.50 to < 3.00 x ULN	≥ 3.00 x ULN
WBC, Decreased (cells/mm ³ ; cells/L)				
> 7 days of age	2,000 to 2,499 2.000 x 10⁹ to 2.499 x 10⁹	1,500 to 1,999 1.500 x 10⁹ to 1.999 x 10⁹	1,000 to 1,499 1.000 x 10⁹ to 1.499 x 10⁹	< 1,000 < 1.000 x 10 ⁹
≤ 7 days of age	5,500 to 6,999 5.500 x 10⁹ to 6.999 x 10⁹	4,000 to 5,499 4.000 x 10⁹ to 5.499 x 10⁹	2,500 to 3,999 2.500 x 10⁹ to 3.999 x 10⁹	< 2,500 < 2.500 x 10 ⁹

Urinalysis

PARAMETER	GRADE 1 MILD	GRADE 2 MODERATE	GRADE 3 SEVERE	GRADE 4 POTENTIALLY LIFE- THREATENING
Glycosuria (random collection tested by dipstick)	Trace to 1+ or ≤ 250 mg	2+ or > 250 to ≤ 500 mg	> 2+ or > 500 mg	NA
Hematuria (not to be reported based on dipstick findings or on blood believed to be of menstrual origin)	6 to < 10 RBCs per high power field	≥ 10 RBCs per high power field	Gross, with or without clots OR With RBC casts OR Intervention indicated	Life-threatening consequences
Proteinuria (random collection tested by dipstick)	1+	2+	3+ or higher	NA

Total Bilirubin Table for Term and Preterm Neonates

PARAMETER	GRADE 1 MILD	GRADE 2 MODERATE	GRADE 3 SEVERE	GRADE 4 POTENTIALLY LIFE- THREATENING
Total Bilirubin¹⁹, High (mg/dL; $\mu\text{mol/L}$) ²⁰				
Term Neonate²¹ < 24 hours of age	4 to < 7 68.4 to < 119.7	7 to < 10 119.7 to < 171	10 to < 17 171 to < 290.7	≥ 17 ≥ 290.7
24 to < 48 hours of age	5 to < 8 85.5 to < 136.8	8 to < 12 136.8 to < 205.2	12 to < 19 205.2 to < 324.9	≥ 19 ≥ 324.9
48 to < 72 hours of age	8.5 to < 13 145.35 to < 222.3	13 to < 15 222.3 to < 256.5	15 to < 22 256.5 to < 376.2	≥ 22 ≥ 376.2
72 hours to < 7 days of age	11 to < 16 188.1 to < 273.6	16 to < 18 273.6 to < 307.8	18 to < 24 307.8 to < 410.4	≥ 24 ≥ 410.4
7 to 28 days of age (breast feeding)	5 to < 10 85.5 to < 171	10 to < 20 171 to < 342	20 to < 25 342 to < 427.5	≥ 25 ≥ 427.5
7 to 28 days of age (not breast feeding)	1.1 to < 1.6 x ULN	1.6 to < 2.6 x ULN	2.6 to < 5.0 x ULN	≥ 5.0 x ULN
Preterm Neonate²⁰ 35 to < 37 weeks gestational age	Same as for Total Bilirubin, High, Term Neonate (based on days of age).	Same as for Total Bilirubin, High, Term Neonate (based on days of age).	Same as for Total Bilirubin, High, Term Neonate (based on days of age).	Same as for Total Bilirubin, High, Term Neonate (based on days of age).
32 to < 35 weeks gestational age and < 7 days of age	NA	NA	10 to < 14 171 to < 239.4	≥ 14 ≥ 239.4
28 to < 32 weeks gestational age and < 7 days of age	NA	NA	6 to < 10 102.6 to < 171	≥ 10 ≥ 171
< 28 weeks gestational age and < 7 days of age	NA	NA	5 to < 8 85.5 to < 136.8	≥ 8 ≥ 136.8
7 to 28 days of age (breast feeding)	5 to < 10 85.5 to < 171	10 to < 20 171 to < 342	20 to < 25 342 to < 427.5	≥ 25 ≥ 427.5
7 to 28 days of age (not breast feeding)	1.1 to < 1.6 x ULN	1.6 to < 2.6 x ULN	2.6 to < 5.0 x ULN	≥ 5.0 x ULN

¹⁹ Severity grading for total bilirubin in neonates is complex because of rapidly changing total bilirubin normal ranges in the first week of life followed by the benign phenomenon of breast milk jaundice after the first week of life. Severity grading in this appendix corresponds approximately to cut-offs for indications for phototherapy at grade 3 and for exchange transfusion at grade 4.

²⁰ A laboratory value of 1 mg/dL is equivalent to 17.1 $\mu\text{mol/L}$.

²¹ Definitions: Term is defined as ≥ 37 weeks gestational age; near-term, as ≥ 35 weeks gestational age; preterm, as < 35 weeks gestational age; and neonate, as 0 to 28 days of age.

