5.2 Adverse Events

Bleeding adverse events

Total number of participants with Type 1, 2, 3, 4 or 5 bleeding episodes using BARC criteria. Bleeding episodes will be summarised by type and randomised treatment.

Serious Adverse Events

Total number of participants with any Serious Adverse Event (SAE) and the cumulative incidence of SAEs. SAEs will be summarised by randomised treatment and relationship to study drug.

Adverse events

Total number of participants with any Adverse event (AE) and the cumulative incidence of AEs. All AEs, and grade 3 or 4 AEs, will be summarised by MedDRA group term, relationship to study drug and randomised treatment.

Laboratory adverse events

Total number of participants with laboratory or biochemical adverse events, according to DAIDS criteria, in particular renal function measured by the CKD-EPI estimate of creatinine clearance. Laboratory AEs will be summarised by grade and randomised treatment.

Statistical analysis of adverse event data

The proportion of patients with adverse events will be compared between randomised treatments using chi-square tests, Fisher's exact test or similar as appropriate to the data. Differences in proportions of patients with events by randomised treatments will be summarised as 95% confidence intervals.

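### Appendix 1 gives adult phosphate limits that differ between mg/dL and mmol/L, and overlapping sodium grades, so a laboratory grade can depend on the reporting unit

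*Protocol*

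**What the plan says.** Protocol Appendix 1 (Chemistries) gives phosphate limits in two units. In the row for ages above 14 years, the only one that applies because Protocol 7.1 requires age 40 or over, the entries in mg/dL and then mmol/L are:

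- Grade 1: "2.0 to < LLN 0.81 to < LLN"
- Grade 2: "1.4 to < 2.0 0.65 to < 0.81"
- Grade 3: "1.0 to < 1.4 0.32 to < 0.65"
- Grade 4: below 1.0 mg/dL, below 0.32 mmol/L

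The two paediatric rows beneath it include "2.5 to < 3.0 0.81 to < 0.97" (Grade 2, 1 to 14 years), "3.5 to < 4.5 1.13 to < 1.45" (Grade 1, under 1 year) and "1.5 to < 2.5 0.48 to < 0.81" (Grade 3, both rows).

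For low sodium, Grade 2 reads "125 to < 130 125 to < 135" in mEq/L and mmol/L. Grade 1 is 130 to <135 in both units.

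Both analytes are in the biochemistry panel at screening and weeks 0, 12 and 18 (Protocol 2.0). They are tested at local laboratories (Protocol 13.5), at about 7 centres in Australia and the USA (Protocol 6.0). SAP 5.2 counts participants with laboratory events by DAIDS criteria and adds: "Laboratory AEs will be summarised by grade and randomised treatment". Neither document names a unit for grading or a conversion step before it.

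**The concern.** A grading table with two unit columns works only if both columns describe the same cut-offs. Here 0.81 mmol/L is set equal to 2.0 mg/dL in the adult row and to 2.5 mg/dL in the two rows below it, so the table contradicts itself. If laboratories report in different units and grades are read from the matching column, the same phosphate result can carry different grades at different sites. The planned tabulation by grade would then have no unique answer and could not be compared between sites. The sodium entry raises a related but different problem: one result satisfies two grades within a single column.

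**Working it through.** **Step 1. The conversion factor, from the table alone.** Factor = mmol/L limit ÷ mg/dL limit.

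| Row | mg/dL | mmol/L printed | Factor |
|---|---|---|---|
| Paediatric | 1.5 | 0.48 | 0.320 |
| Paediatric | 2.5 | 0.81 | 0.324 |
| Paediatric | 3.0 | 0.97 | 0.323 |
| Paediatric | 3.5 | 1.13 | 0.323 |
| Paediatric | 4.5 | 1.45 | 0.322 |
| Adult | 1.0 | 0.32 | 0.320 |
| Adult | 1.4 | 0.65 | 0.464 |
| Adult | 2.0 | 0.81 | 0.405 |

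All paediatric pairs and the adult 1.0 mg/dL pair lie between 0.320 and 0.324. The other two adult pairs do not.

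**Step 2. The adult limits put on a common footing (factor 0.323).**

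- From mg/dL: 2.0 × 0.323 = 0.646; 1.4 × 0.323 = 0.452; 1.0 × 0.323 = 0.323 mmol/L. With factors of 0.320 to 0.324 the first two are 0.640 to 0.648 and 0.448 to 0.454.
- From mmol/L: 0.81 ÷ 0.323 = 2.51; 0.65 ÷ 0.323 = 2.01; 0.32 ÷ 0.323 = 0.99 mg/dL.
- Relative to the converted mg/dL limits, the printed mmol/L limits are 0.81 ÷ 0.646 = 1.25 times and 0.65 ÷ 0.452 = 1.44 times as high. The third agrees within rounding.

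**Step 3. The same result graded in both columns.**

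| Phosphate, mmol/L | mg/dL | mg/dL column | mmol/L column |
|---|---|---|---|
| 0.40 | 1.24 | Grade 3 | Grade 3 |
| 0.50 | 1.55 | Grade 2 | Grade 3 |
| 0.60 | 1.86 | Grade 2 | Grade 3 |
| 0.70 | 2.17 | Grade 1 if below LLN, otherwise ungraded | Grade 2 |

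The columns disagree from about 0.45 to <0.65 mmol/L (Grade 2 against Grade 3) and from 0.65 to <0.81 mmol/L (Grade 1 or ungraded against Grade 2). Elsewhere they agree, apart from rounding near 0.32.

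**Step 4. Sodium.** For sodium, mEq/L and mmol/L are numerically equal, and the other low-sodium grades are printed identically in both. In mEq/L a value of 132 is Grade 1 only. In mmol/L it lies in 130 to <135 (Grade 1) and also in 125 to <135 (Grade 2). Appendix 1's choose-the-higher rule covers clinical events, and laboratory values graded as multiples of the ULN or LLN. It does not cover this case.

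**Step 5. How many results could be affected.** The documents give no phosphate distribution. As an assumption only, take a normal distribution with mean 0.90 to 1.05 and SD 0.15 to 0.20 mmol/L. The share at Grade 3 or higher is then the share below 0.65 (mmol/L column) or below 0.452 (mg/dL column):

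- mean 0.90, SD 0.20: 10.6% against 1.3%
- mean 0.95, SD 0.18: 4.8% against 0.3%
- mean 1.05, SD 0.15: 0.4% against 0.0%

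In the middle case, for 60 participants, that is 60 × 0.048 = 2.9 against 60 × 0.003 = 0.2 per visit, and only if every site used mmol/L. The ratio between columns runs from about 8 to over 100 across this range, so no single ratio should be quoted.

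**The case against.** The arithmetic cannot be disputed, and the cells are complete and in sequence, so a PDF reading fault is unlikely. The case on the other side concerns consequence, and much of it stands.

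- **Recording.** Protocol 11.1 tells sites that, as a rule, a laboratory abnormality on its own, without clinical features, is not recorded as an adverse event. This limits how many low phosphates sites would record as adverse events. It does not remove the problem, because SAP 5.2 still plans a laboratory summary by DAIDS grade; the two texts themselves need reconciling.
- **Arm comparison.** A reader might infer bias between treatments. The documents do not support that. Randomisation is 1:1 within site (Protocol 8.0), so both arms share the local laboratory's practice. The protocol's biochemistry endpoint is change from baseline (Protocol 5.5), which uses no grade limits.
- **Direction.** A reader might infer that Grade 3 hypophosphataemia is overstated at sites using SI units. That presumes the mg/dL limits are the intended ones. If the mmol/L limits are intended, the mg/dL column understates instead. Nothing in the documents decides this.
- **Management.** A reader might infer that the discrepancy runs through all of Protocol 10.2. It does not. Grades 1 and 2 share one rule (10.2.1), and the Grade 4 limit agrees in both units. Only Grade 2 against Grade 3 matters, and 10.2.2 leaves withholding for drug-related Grade 3 events to the investigator's discretion.
- **Sodium.** This is an ambiguity. It gives a higher grade only if someone resolves the overlap upward.

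**Conclusion.** The inconsistency is real and is shown by the table's own rows. Two of the three adult phosphate cut-offs differ between units, and one sodium band meets two grades. The affected results are phosphate from about 0.45 to <0.81 mmol/L and sodium from 130 to <135 mmol/L. The consequence is confined to the SAP 5.2 laboratory summary, whose grade counts would depend on the local unit and would not be comparable between sites, and to the discretionary Grade 3 text in Protocol 10.2.2.

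The conclusion that arms are not systematically biased rests on the site-stratified randomisation and on each site's laboratory treating both arms alike. The primary endpoint does not use these grades. The documents do not state the intended phosphate limits, the reporting unit at any site, the handling of units in the eCRF, or the phosphate distribution. The direction and size of any misgrading are therefore unknown, and the percentages above only illustrate a range. Severity is minor.

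**What to change.** 1. Check the phosphate and sodium rows of Appendix 1, in both units, against the DAIDS Version 2.0 source table and correct whichever entries differ. This review does not say which limits are right.
2. Add a sentence to SAP 5.2: all phosphate and sodium results are converted to one stated unit and graded centrally by program on the reconciled limits, for all sites, before database lock.
3. If sites have already assigned grades for these two analytes, re-derive them in the same way.
4. Reconcile SAP 5.2 with Protocol 11.1 by stating whether the laboratory summary is built from all laboratory results or only from events that sites recorded.

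The cost is small: two corrected table lines, one or two SAP sentences and a unit conversion in the grading program. No new data are needed if the reporting unit has been recorded with each result; otherwise it must be confirmed with each site.
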